10.1.4.1.2. Statistical Methodology Specification for Part B (Repeat Dose)

Pharmacodynamic Statistical Analyses – Mixed Effect Model – Repeat Dose (Part B)
Endpoint / Variables
tPGDM, tPGEM, Creatinine, Creatinine corrected tPGDM and Creatinine corrected tPGEM (Aggregated values for predose 24-12hr & 12-0hr and postdose 0-12 hr, 12-24 hr & 24-48 hr)
Model Specification
Log _e transformed values of the endpoints will be statistically analyzed using Mixed Model (MM).

 • Fixed effect: timepoint, dose, timepoint*dose • Random effect: Subject
An unstructured covariance structure for the G matrix will be used.

 • If this model fails to converge, alternative covariance structures may be considered. • Akaike’s Information Criteria (AIC) will be used to assist with the selection of covariance structure.
Analyses will be done with the MIXED Procedure in SAS, using the Kenward-Roger option to estimate denominator degrees of freedom and standard errors
Model Checking & Diagnostics

 • For the Mixed Model, model assumptions will be checked, and appropriate adjustments may be applied based on the data. • Distributional assumptions underlying the model used for analysis will be examined by obtaining a normal probability plot of the residuals and a plot of the residuals versus the fitted values (i.e. checking the normality assumption and constant variance assumption of the model respectively) to gain confidence that the model assumptions are reasonable. • If there are any departures from the distributional assumptions, alternative transformations, such as data squared or square root of data, will be explored. • Non-parametric analyses will be conducted if the normality assumption does not hold.
Model Results Presentation
LS Geometric means and 90% CI are estimated for each dose as well as the estimate (90% CI) of change from baseline for each timepoint, using the time matched baseline.
Note: For post dose 24-48hrs baseline (predose) is not available
Consider Day -1(predose), Day1, Day 7, Day 10, Day 17

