9. STATISTICAL CONSIDERATIONS

9.1. Statistical Hypotheses

The primary objectives of this study are to evaluate safety and tolerability of single and repeat doses of GSK3439171A and to characterize the PK of GSK3439171A. No formal statistical hypotheses will be tested. Descriptive statistics will be used to assess safety and tolerability objectives. Treatment comparisons with placebo will be based on review of descriptive statistics and individual participant data. An estimation approach will be used to address the PK objectives where point estimates and corresponding 90% confidence intervals (CIs) will be constructed as appropriate for the assessment of dose-proportionality, steady-state, time invariance and food effect.

Estimation of effects of GSK3439171A on PD/biomarkers is an exploratory objective. No formal statistical hypotheses will be tested. An estimation approach will be used to address these objectives, where point estimates and corresponding CIs will be constructed as appropriate.

Unblinded, in-stream data reviews will be performed for Parts A and B in order to inform dose-escalation decisions. Final results for each study part (A, B, C) may be reported as each part completes rather than after completion of all study parts.

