9.4.2. Other Analyses

In Parts A and B, dose-response modelling of urinary tPGDM/tPGEM will be undertaken, data permitting. Details will be described in the reporting and analysis plan. The population PK analysis and pharmacodynamic analyses may be presented separately from the main clinical study report (CSR).

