10. PHARMACODYNAMIC (AND / OR BIOMARKER) ANALYSES

10.1. Exploratory Pharmacodynamic and Biomarker Analyses

10.1.1. Endpoint / Variables

Following table describes the pharmacodynamic/biomarker end points:

Parameter	Parameter Description/Derivation	Part A	Part B
PGD2			X
PGE2			X
Creatinine #		X	X
tPGDM #		X	X
tPGEM #		X	X
6-keto-PGF1A			X
PGF2A			X
TXB2			X
Creatinine corrected data for tPGDM and tPGEM #	Three versions of data to be considered: 1.Raw data(mass) 2. Aggregated data 0-12hrs 3. Aggregated data 12-24hr 4. Aggregated data 24-48hrs Each version of data(mass) divided by time matched creatinine(mass)	X	X
Baseline corrected urinary tetranor data for tPGDM and tPGEM #	Post dose data divided by time matched baseline data Three versions of data to be considered: 1.Creatinine corrected raw data 2. Creatinine corrected aggregated data 0-12hrs 3. Creatinine corrected aggregated data 12-24hrs	X	X
Baseline corrected urinary tetranor data for creatinine #	Post dose data divided by time matched baseline data Three versions of data to be considered: 1.Raw data 2. Aggregated data 0-12hrs 3. Aggregated data 12-24hrs	X	X

Parameter	Parameter Description/Derivation	Part A	Part B
Placebo corrected data for tPGDM and tPGEM #	
Creatinine corrected data from active dose divided by time matched placebo data and then find ratio to baseline.
 
Three versions of data to be considered:
 
 1.Creatinine corrected raw data 2. Creatinine corrected aggregated data 0-12hrs 3. Creatinine corrected aggregated data 12-24hrs 	X	
Placebo corrected data for creatinine #	
Data from active dose divided by time matched placebo data and then find ratio to baseline.
 
Three versions of data to be considered:
 
 1.Raw data 2. Aggregated data 0-12hrs 3. Aggregated data 12-24hrs 	X	
Time matched PK Concentration for urinary tetranor data for tPGDM and tPGEM	
For each PD marker interval, use the upper bound as target time; e.g. for 0-2hr interval, 2hr is the target time
 
Identify PK concentration with nominal time at the target time;
 
If there is no PK sample taken at target time, use the PK concentration data with nominal time before but closest to target time;
 
Use 0 PK concentration for placebo
	X	X

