11. PHARMACOKINETIC / PHARMACODYNAMIC ANALYSES

A detailed population PK/PD data analysis plan will be prepared in a separate RAP.

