13.12.9. Pharmacodynamic (and / or Biomarker) Tables

Pharmacodynamic (and or Biomarker): Tables					
No.	Population	IDSL / Example Shell	Title	Programming Notes	Deliverable [Priority]
Urinary Tetranor and Urinary Creatinine					
6.1.	PD	PK03	Summary Statistics of Urinary Tetranor and Urinary Creatinine Concentration Data– Part A		SAC

Pharmacodynamic (and or Biomarker): Tables					
No.	Population	IDSL / Example Shell	Title	Programming Notes	Deliverable [Priority]
6.2.	PD	PK03	Summary Statistics of Urinary Tetranor and Urinary Creatinine Parameters – Part A	
PD parameters: tPGDM, tPGEM End points #:
 
 1)Raw data (mass) 2)Creatinine corrected raw data, 3)Creatinine corrected aggregated data 0-12hrs, 4)Creatinine corrected aggregated data 12-24hrs 5)Creatinine corrected aggregated data 24-48hrs Baseline corrected value, Placebo corrected value and ratio of tPGDM/tPGEM for version 2,3 & 4 of the data mentioned above 
PD parameters: Creatinine End points #:
 
 1)Raw data (mass), 2)Aggregated data 0-12hrs & 3)Aggregated data 12-24hrs 4) Aggregated data 24-48hrs 
Baseline corrected value and Placebo corrected value for version 2,3 & 4 of the data mentioned above
	SAC
6.3.	PD	PK03	Summary Statistics of Urinary Tetranor and Urinary Creatinine Concentration Data – Part B		SAC

Pharmacodynamic (and or Biomarker): Tables					
No.	Population	IDSL / Example Shell	Title	Programming Notes	Deliverable [Priority]
6.4.	PD	PK03	Summary Statistics of Urinary Tetranor and Urinary Creatinine Parameters – Part B	
PD parameters: tPGDM, tPGEM End points #:
 
 1)Raw data (mass) 2)Creatinine corrected raw data, 3)Creatinine corrected aggregated data 0-12hrs, 4)Creatinine corrected aggregated data 12-24hrs 5)Creatinine corrected aggregated data 24-48hrs Baseline corrected value and ratio of tPGDM/tPGEM for version 3,4 & 5 of the data mentioned above 
PD parameters: Creatinine End points #:
 
 1)Raw data (mass) 2)Aggregated data 0-12hrs & 3)Aggregated data 12-24hrs 4)Aggregated data 24-48hrs 
Baseline corrected value and Placebo corrected value for version 2,3 & 4 of the data mentioned above
	SAC

Pharmacodynamic (and or Biomarker): Tables					
No.	Population	IDSL / Example Shell	Title	Programming Notes	Deliverable [Priority]

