6.14.	PD	LB_PLOT1	Plot of Ratio of Urinary Tetrano Parameters vs Time by Subject- Part B	
Ratios of PD parameters to consider: tPGDM/tPGEM for Day 1, 7, 9, 10 & 17
 
End points #:
 
 • 1)Creatinine corrected raw data, 2)Creatinine corrected aggregated data 0-12hrs, 3)Creatinine corrected aggregated data 12-24hrs 4)Creatinine corrected aggregated data 24-48hrs • Time matched ratio for above mentioned 4 versions of data 
Note: Each line(profile) for each day. Data available on day 1 for all cohorts, day 7 & 10 for cohort 3 only, day 9 &17 for cohort 1&2.
	SAC

Pharmacodynamic: Figures					
No.	Population	IDSL / Example Shell	Title	Programming Notes	Deliverable [Priority]
6.15.	PD	LB_PLOT2	Geometric mean and 95% CI Ratio of Urinary Tetranor Parameters vs time – Part A	
Ratios of PD parameters to consider: tPGDM/tPGEM
 
End points #:
 
 1)Creatinine corrected raw data, 2)Creatinine corrected aggregated data 0-12hrs, 3)Creatinine corrected aggregated data 12-24hrs 4)Creatinine corrected aggregated data 24-48hrs 
 Time matched ratio for above mentioned 4 versions of data 
Note: X-axis values – actual midpoint of collection
	SAC

Pharmacodynamic: Figures					
No.	Population	IDSL / Example Shell	Title	Programming Notes	Deliverable [Priority]
6.16.	PD	LB_PLOT2	Geometric mean and 95% CI Ratio of Urinary Tetranor Parameters vs time – Part B	
Ratios of PD parameters to consider: tPGDM/tPGEM for Day 1, 7, 9, 10 & 17
 
End points #:
 
 1)Creatinine corrected raw data, 2)Creatinine corrected aggregated data 0-12hrs, 3)Creatinine corrected aggregated data 12-24hrs 4)Creatinine corrected aggregated data 24-48hrs 
 Time matched ratio for above mentioned 4 versions of data 
Note: Panel plot with each panel for each day. Data available on day 1 for all cohorts, day 7 & 10 for cohort 3 only, day 9 & 17 for cohort 1&2.
	SAC

#Refer to Section 10.1.1 for derivation of PD endpoints

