 Population : Pharmacokinetic

Table PK_T5

Statistical Analysis of log transformed plasma GSKxxx Pharmacokinetic Parameters Assessing Accumulation Ratio and Time Invariance – Part B

Treatment	Parameter (units) :	Comparison	Geom.LsMean		Ratio	90% Confidence Interval		
			n Test	n Ref				
XXmg	AUC (Ro) (µg.h/mL)	Day 17 vs Day 1	XX	x.xxx	xx	x.xxx	x.xxx	(x.xxx, x.xxx)
	Cmax (RCmax) (µg/mL)	Day 17 vs Day 1	XX	x.xxx	xx	x.xxx	x.xxx	(x.xxx, x.xxx)
	AUC (Res) (µg.h/mL)	Day 17 vs Day 1	XX	x.xxx	xx	x.xxx	x.xxx	(x.xxx, x.xxx)

Example : PK_T6
Protocol : GSKxxx
Population : Pharmacokinetic

Table PK_T6

Statistical Analysis of log transformed plasma GSKxxx Pharmacokinetic Parameters Assessing Achievement of Steady State– Part B

Parameter	Treatment	Day	Back-Transformed Slope	90% Confidence Interval
C trough	xxmg	1-17	x.xxx	(x.xxx, x.xxx)
	xxmg	1-17	x.xxx	(x.xxx, x.xxx)

Example : PD_T1
 Protocol : GSKxxx
 Population : Pharmacodynamic

Page 1 of n

Table
 Statistical Analysis of Urinary Tetrator and Urinary Creatinine Parameters:
 Mixed Effect Model - Part A

Parameter: tPGEM

Visit		Placebo (N=xxx)	Dose1 (N=xxx)	Dose6 (N=xxx)
Day -1, 24-12hr	n	xxx	xxx	xxx
	Adjusted Geometric Mean	x.xxx	x.xxx	x.xxx
	90% C.I.	(x.xxx, x.xxx)	(x.xxx, x.xxx)	(x.xxx, x.xxx)
Day -1, 12-0hr	n	xxx	xxx	xxx
	Adjusted Geometric Mean	x.xxx	x.xxx	x.xxx
	90% C.I.	(x.xxx, x.xxx)	(x.xxx, x.xxx)	(x.xxx, x.xxx)
Day 1, 0-12hr	n	xxx	xxx	xxx
	Adjusted Geometric Mean	x.xxx	x.xxx	x.xxx
	90% C.I.	(x.xxx, x.xxx)	(x.xxx, x.xxx)	(x.xxx, x.xxx)
	Change from Baseline	x.xxx	x.xxx	x.xxx
	90% C.I.	(x.xxx, x.xxx)	(x.xxx, x.xxx)	(x.xxx, x.xxx)
Day 1, 12-24hr	n	xxx	xxx	xxx
	Adjusted Geometric Mean	x.xxx	x.xxx	x.xxx
	90% C.I.	(x.xxx, x.xxx)	(x.xxx, x.xxx)	(x.xxx, x.xxx)

Change from Baseline	x.xxx	x.xxx	x.xxx
90% C.I.	(x.xxx, x.xxx)	(x.xxx, x.xxx)	(x.xxx, x.xxx)
Day 1, 24-48hr	n	xxx	xxx
Adjusted Geometric Mean	x.xxx	x.xxx	x.xxx
90% C.I.	(x.xxx, x.xxx)	(x.xxx, x.xxx)	(x.xxx, x.xxx)

Example OT_L1

Protocol : GSKxxx
Population : Screened

Listing 11
Listing of Re-screened Subjects

Part	Unique Subject Id.	First Screening Number	Second Screening Number
Part A	XXXXXX.XXXXXX	XXXXXX	XXXXXX
	XXXXXX.XXXXXX	XXXXXX	XXXXXX
	XXXXXX.XXXXXX	XXXXXX	XXXXXX

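### The Part B PD model reports change from baseline per dose, but no tPGDM/tPGEM output gives a placebo-adjusted estimate with an interval

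*SAP*

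**What the plan says.** Protocol 9.1 sets the aim: "Estimation of effects of GSK3439171A on PD/biomarkers is an exploratory objective", to be met with point estimates and CIs and no hypothesis test.

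SAP 10.1.4.1.2 (Part B) fits timepoint, dose and their interaction with a random subject effect. For each dose it presents LS geometric means with 90% CI and the estimate with 90% CI "of change from baseline for each timepoint, using the time matched baseline". SAP 10.1.4.1.1 (Part A) presents the same outputs. Shell PD_T1 in SAP 13.13, used for Tables 6.8 and 6.9, has a placebo column beside the dose columns and a row for "Change from Baseline". It has no row or column for active against placebo.

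Outside the models, SAP 10.1.1 defines placebo-corrected tPGDM/tPGEM as "Creatinine corrected data from active dose divided by time matched placebo data and then find ratio to baseline" and marks it for Part A only. For Part B, Table 6.4 lists for these two markers "Baseline corrected value and ratio of tPGDM/tPGEM for version 3,4 & 5 of the data mentioned above". Its only placebo-corrected entry is for creatinine, which 10.1.1 also marks for Part A only.

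SAP 5.1 lists dose-versus-placebo and repeat-dose-versus-placebo among the treatment comparisons to be displayed, but no PD model output or listed PD display takes them up.

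**The concern.** A change from baseline within one dose group estimates the drug effect plus whatever else moved between Day -1 and the later day. The randomised placebo participants supply that second part. They are already in the same model, but it is never asked to subtract it. A reader of Table 6.9 can compare two columns by eye and has no interval for the difference.

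The protocol's stated aim is to estimate effects of the drug, and Part B is randomised and placebo-controlled. As an example, with assumed values: if active falls to 0.70 of baseline, the reported change is 0.70 whether placebo moves to 0.80 or to 1.20. The placebo-adjusted ratio is 0.70/0.80 = 0.875 in the first case and 0.70/1.20 = 0.583 in the second.

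Part A's subject-level division by placebo has no direct counterpart in the parallel Part B, where participants have no placebo period of their own. A model contrast does.

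**Working it through.** **1. Trace of the tPGDM/tPGEM outputs.** The plan has no figure to reproduce here; Protocol 9.2 says the sample size does not rest on statistical considerations.

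| Output | Part A | Part B |
|---|---|---|
| Placebo-corrected endpoint (SAP 10.1.1) | marked | not marked |
| Summary table | 6.2: baseline- and placebo-corrected | 6.4: baseline-corrected and analyte ratio; placebo-corrected for creatinine only |
| Geometric mean with 95% CI | Figure 6.5: includes placebo-corrected | Figure 6.6: baseline-corrected only |
| Mixed model | 6.8: change from baseline | 6.9: change from baseline |
| Other figures | 6.1, 6.3, 6.7, 6.9: include placebo-corrected | 6.2, 6.4, 6.8, 6.10: baseline-corrected; 6.12, 6.14, 6.16: analyte ratio |

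**2. Inputs for the illustration.** Part B has 9 active and 3 placebo in each of 3 cohorts (Protocol 9.2). Sampling days follow the Figure 6.2 note: Day 1 for all cohorts, Days 9 and 17 for cohorts 1-2, Days 7 and 10 for cohort 3. The SD of log change is not given; 0.3 is assumed, and 0.2 to 0.5 is used as a range. The background fall is also assumed.

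**3. Degrees of freedom (Part B, one pooled placebo level).** Each participant has two 12-hour windows on Day -1, Day 1 and two later days, so 36 × 8 = 288 values. Subtract 36 subjects, 3 × 7 = 21 for the active doses and 11 for placebo (12 timepoints less 1): 288 - 36 - 21 - 11 = 220. Then t(0.95) is about 1.652.

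**4. Interval factors.** SE = 0.3 × sqrt(1/n_active + 1/n_placebo), or 0.3/sqrt(n) for change alone. Factor = exp(1.652 × SE). The fall needed for the CI to exclude 1 is 1 - 1/factor.

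| Estimate | SE | ×/÷ factor | Fall needed |
|---|---|---|---|
| Part B change alone, n = 9 | 0.100 | 1.18 | 15% |
| 9 vs 9 (Day 1) | 0.1414 | 1.26 | 21% |
| 9 vs 6 (Days 9, 17) | 0.1581 | 1.30 | 23% |
| 9 vs 3 (cohort 3 on Days 7, 10, or own cohort) | 0.200 | 1.39 | 28% |
| Part A change alone, n = 6 | 0.1225 | 1.22 | 18% |
| Part A, 6 vs 18 | 0.1414 | 1.26 | 21% |

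The Part A row takes two cohorts of nine, from the six doses listed in SAP 5.1, with one placebo period each.

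**5. Change alone when the drug does nothing.** P(upper 90% limit < 1) from the noncentral t, with noncentrality ln(1 - fall)/(SD/3) and 200 df. At SD 0.3, the noncentrality is ln(0.9)/0.1 = -1.05 for a 10% fall and ln(0.8)/0.1 = -2.23 for a 20% fall. The probabilities are 28% and 72%, against 5% with no fall. Over SD 0.2 to 0.5 they run from 47% to 16% and from 96% to 38%.

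**6. What the contrast removes.** If the fall is common to all cohorts, the 9 vs 9 contrast stays at 5% (simulated: 5.1%, 4.9% and 5.0% for falls of 0, 10% and 20%). If it occurs only in the active group's own cohort, three of the nine pooled placebo participants share it and six do not, so two thirds of it remains: (2/3) × ln(0.9)/0.1414 = -0.50 and (2/3) × ln(0.8)/0.1414 = -1.05. The probabilities are then 12.5% and 27.5%. The own-cohort contrast (9 vs 3) removes this remainder, at twice the SE of change alone (0.200 against 0.100).

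**The case against.** The strongest reply is that the intent is already written down. SAP 5.1 names the placebo comparisons. The PK models compare doses, days or fed with fasted, and safety is descriptive only, so the PD models are the only ones to which such a comparison could attach. SAP 13.13 also says its shells are examples and not study specific. This stands in part. It reduces the gap to a comparison announced but not carried into 10.1.4.1.2 or Table 6.9, and both places list their outputs without it.

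Second, other features limit the harm. Placebo has its own column and CI, baselines are time-matched, creatinine correction is applied, and Figure 6.16 gives "Geometric mean and 95% CI Ratio of Urinary Tetranor Parameters vs time". The analyte ratio removes shifts common to both markers, but only those, and it is not compared with placebo.

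Third, Protocol 9.4.2 says "dose-response modelling of urinary tPGDM/tPGEM will be undertaken, data permitting", and SAP 11 says "A detailed population PK/PD data analysis plan will be prepared in a separate RAP". Either may use placebo. This SAP contains no such modelling, and the separate plan was not supplied.

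A reader might infer three stronger things that the documents do not support:

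- That no PD output anywhere is placebo-adjusted with a CI. Figure 6.5 provides this for Part A, outside the model.
- That a placebo contrast guarantees a 5% rate. It does so only for shifts common to the cohorts being pooled, and Part B cohorts run one after another.
- That the 14-day schedule restricts post-Day 1 urine PD to Day 10. That wording is a footnote on the Days 9-11 column of a table that did not extract cleanly, so it may only say which of those days applies.

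**Conclusion.** The gap is real and modest. In Part B, no tPGDM/tPGEM output in this SAP gives a placebo-adjusted estimate with a CI, although the control data and the model are both in place and SAP 5.1 names the comparison. In Part A the same omission from Table 6.8 is mainly a matter of consistency.

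The 28% and 72% figures show how a shared shift could be misread. They rest on an assumed SD and an assumed background fall, and the documents give no evidence that such a fall will occur. The endpoint is exploratory, no hypothesis is tested and no rule depends on whether an interval excludes 1. This is therefore an improvement worth considering; it does not threaten the trial's primary objectives.

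**What to change.** Carry the SAP 5.1 comparison into 10.1.4.1.2 and Table 6.9 and, for consistency, into 10.1.4.1.1 and Table 6.8. For each dose and each timepoint with a time-matched baseline (so not 24-48 hr), add beside the change from baseline the ratio exp[(post - baseline) dose - (post - baseline) placebo] on the log scale, with its 90% CI. In Part A use all placebo periods.

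For Part B, state the placebo comparator by day: placebo participants from the cohorts sampled that day, with baseline from the same participants, pooled across cohorts where the day is shared. Show the own-cohort contrast (9 vs 3) as a check. One way is to enter placebo by cohort as separate levels and average them by number of participants. On Day 1 the variance multiplier is 1/9 + 3 × (1/3)²/3 = 1/9 + 1/9, so the SE is still 0.1414. The residual df become 288 - 36 - 21 - 21 = 210, which leaves the factors unchanged. SAP 5.1 already codes cohort 3 placebo separately.

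Two clarifications belong with this. First, confirm the urine PD days: SAP 10.1.4.1.2 lists post-dose Days 1, 7, 10 and 17, while the Figure 6.2 note has Days 1, 9 and 17 for cohorts 1-2 and Days 1, 7 and 10 for cohort 3, so Day 9 is in one and not the other. Second, align the placebo-correction rows of 10.1.1 with Table 6.4.

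The cost is a few contrast statements, the added table rows and the wider intervals shown in the working. Taking the placebo baseline only from participants sampled that day adds little: SE 0.158 instead of 0.152 (9 vs 6) and 0.200 instead of 0.180 (9 vs 3). No new data are needed, and the planned change from baseline stays in the table.

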11. PHARMACOKINETIC / PHARMACODYNAMIC ANALYSES

A detailed population PK/PD data analysis plan will be prepared in a separate RAP.

13. APPENDICES

13.1. Appendix 1: Protocol Deviation Management and Definitions for Per Protocol Population

As Per Protocol Population is not defined, this section is not applicable.

13.2. Appendix 2: Schedule of Activities

13.2.1. Protocol Defined Schedule of Events

SoA – Part A

Part A- Single Dose										
Procedure	Screening (up to 30 days before Day 1)	Treatment Period [Days] (for each dosing period)						E.D.	Follow-up (~14±1 days post last dose)	Notes E.D = early discontinuation/withdrawal
		-2	-1	1	2	3	4			
Informed consent	X									
Inclusion and exclusion criteria (including drug screens)	X			X						Recheck clinical status before randomization and/or 1st dose of study medication.
Demography	X									
Physical examination including height and weight	F	B					B	(B)	F	F: Full exam; B: Brief Exam; height is only taken once at screening

Part A- Single Dose										
Procedure	Screening (up to 30 days before Day 1)	Treatment Period [Days] (for each dosing period)						E.D.	Follow-up (~14±1 days post last dose)	Notes E.D = early discontinuation/withdrawal
		-2	-1	1	2	3	4			
Medical history (includes substance usage and family history of premature cardiovascular (CV) disease and any changes in health status occurring between screening and admission to the unit)	X	X								Substances: Drugs, Alcohol, tobacco, and caffeine
Past and current medical conditions	X	X								
Human Immunodeficiency Virus (HIV), Hepatitis B and C screening	X									If test otherwise performed within 3 months prior to first dose of study intervention, testing at screening is not required
Admission to Clinical Unit		X								
Safety Laboratory assessments (include liver chemistries)	X	X		X	X	X	X	(X)	X	Predose; 8 hr, 24 hr, and, 48 hr, and 72 hr post-dose and at follow-up visit
Routine Urinalysis	X			X	X	X	X	(X)	X	Predose; 8 hr, 24 hr, 48 hr, and 72 hr post-dose and at follow-up visit

Part A- Single Dose										
Procedure	Screening (up to 30 days before Day 1)	Treatment Period [Days] (for each dosing period)						E.D.	Follow-up (~14±1 days post last dose)	Notes E.D = early discontinuation/withdrawal
		-2	-1	1	2	3	4			
12-lead Electrocardiogram (ECG)	X	X		←-----X-----→			(X)	X	ECGs assessed at screening (triplicate) and admission (single). During treatment period ECGs assessed predose (triplicate at least 5 minutes (min) intervals) and single measurements postdose every 30 min for 1 hr, hourly up to 6 hr, and at 12 hr, 24 hr, 36 hr and 48 hr and 72 hr post-dose	
Vital signs (pulse rate, blood pressure (bp), respiratory rate, and oral temperature)	X	X		←-----X-----→			(X)	X	Vitals assessed at screening (triplicate measurements for pulse and (bp)) (and admission (single measurements)). During treatment period vitals assessed predose (triplicate measurements for pulse and bp) and postdose (single measurements) every 15 min for 1 hr, hourly up to 6 hr, then at 12 hr, 24 hr, 36 hr, 48 hr, and 72 hr post-dose. See Section 8.2.2 for further information	
Randomization				X					Randomization will occur before first dose in period 1.	

Part A- Single Dose										
Procedure	Screening (up to 30 days before Day 1)	Treatment Period [Days] (for each dosing period)						E.D.	Follow-up (~14±1 days post last dose)	Notes E.D = early discontinuation/withdrawal
		-2	-1	1	2	3	4			
Genetic sample				X						Any time predose on Day 1. This research may be described in a separate Informed Consent Form (ICF) or as part of a combined ICF. A separate signature is required where participant participation is optional
Study intervention				X						
Telemetry				X						Telemetry performed starting 30 min (±10 min) pre-dose to 12 hr (±20 min) post-dose
Adverse Event (AE) review				←-----X-----→				(X)	X	
Serious Adverse Event (SAE) review	X	←-----X-----→						(X)	X	
Concomitant medication review	X	←-----X-----→						(X)	X	

Part A- Single Dose										
Procedure	Screening (up to 30 days before Day 1)	Treatment Period [Days] (for each dosing period)						E.D.	Follow-up (~14±1 days post last dose)	Notes E.D = early discontinuation/withdrawal
		-2	-1	1	2	3	4			
24hr urine sampling for Pharmacodynamics (PD)			X ¹	X ²	X ³	X ³		(X)		¹ combined void for windows of 24-22 hr, 22-20 hr, 20-18 hr, 18-16 hr, 16-12 hr, and 12-0 hr predose. ² combined void for windows of 0-2 hr, 2-4 hr, 4-6 hr, 6-8 hr 8-12 hr, and 12-24 hr post-dose ³ combined void for 24 hr
Blood sampling for Pharmacokinetics (PK)				←=====X=====→				(X)		Predose, 5min, 30min, 1 hr, 1.5 hr, 2 hr, 3 hr, 4 hr, 6 hr, 8 hr, 10 hr, 12 hr, 18 hr, 24 hr, 36 hr, and 48 hr, 60 hr, and 72 hr post-dose
24 hr Holter Monitoring				X						Predose through 24 hr post-dose
Discharge from Clinical Unit							X	(X)		

The timing and number of planned study assessments, including safety, PK, PD/biomarker or other assessments may be altered during the course of the study based on newly available data (e.g., to obtain data closer to the time of peak plasma concentrations) to ensure appropriate monitoring.

Any changes in the timing or addition of time points for any planned study assessments as the result of emerging pharmacokinetic/pharmacodynamic data from this study must be documented and approved by the relevant study team member and then archived in the sponsor and site study files, but will not constitute a protocol amendment. The Competent Authority (CA) and ethics committee (EC) will be informed of any safety issues that constitute a substantial amendment and require alteration of the safety monitoring scheme or amendment of the ICF. The changes will be approved by the CA and the EC before implementation.

SoA – Part B

Part B – Repeat Dose																							
Procedure	Screening (up to 30 days before Day 1)	Intervention Period [Days] (for each dosing cohort)																	E.D	Follow-up (~14±1 days post last dose)	Notes E.D = early discontinuation/withdrawal		
		-2	-1	1	2	3	4	5-7	8	9-11	12	13-14	15	16	17	18	19	20					
Informed consent	X																						
Inclusion and exclusion criteria (including drug screens)	X	X																				Recheck clinical status before randomization and prior to muscle biopsy/or 1st dose of study medication.	
Demography	X																						
Full physical examination including height and weight	F	B																		B	(B)	F	F: Full exam; B: Brief exam; height is only taken once at screening
Medical history (includes substance usage and family history of premature CV disease and any changes in health status occurring between screening and admission to the unit)	X	X																					Substances: Drugs, Alcohol, tobacco, and caffeine

Part B – Repeat Dose																						
Procedure	Screening (up to 30 days before Day 1)	Intervention Period [Days] (for each dosing cohort)																	E.D	Follow-up (~14±1 days post last dose)	Notes E.D = early discontinuation/withdrawal	
		-2	-1	1	2	3	4	5-7	8	9-11	12	13-14	15	16	17	18	19	20				
Past and current medical conditions	X	X																				
HIV, Hepatitis B and C screening	X																				If test otherwise performed within 3 months prior to first dose of study intervention, testing at screening is not required	
Admission to Clinical Unit		X																				
Safety Laboratory assessments (include liver chemistries)	X	X			X			X ¹		X ¹						X ¹			X	(X)	X ¹	Pre-randomization assessments for eligibility must be performed PRIOR to predose muscle biopsy Predose, 24 hr, and 48, and 72 hr post-Day 1 dose; additional timepoints may be added based on findings in Part A ¹ Days 7, 11, 17, 20, and follow-up

Part B – Repeat Dose																						
Procedure	Screening (up to 30 days before Day 1)	Intervention Period [Days] (for each dosing cohort)																	E.D	Follow-up (~14±1 days post last dose)	Notes E.D = early discontinuation/withdrawal	
		-2	-1	1	2	3	4	5-7	8	9-11	12	13-14	15	16	17	18	19	20				
Routine urinalysis	X	X		X				X ²		X ²					X ²				X ²	(X)	X ²	Predose, 24 hr, 48 hr, and 72 hr post-Day 1 dose; additional timepoints may be added based on findings in Part A ² Days 7, 11, 17, 20, and follow-up

Part B – Repeat Dose																						
Procedure	Screening (up to 30 days before Day 1)	Intervention Period [Days] (for each dosing cohort)																E.D	Follow-up (~14±1 days post last dose)	Notes E.D = early discontinuation/withdrawal		
		-2	-1	1	2	3	4	5-7	8	9-11	12	13-14	15	16	17	18	19				20	
Vital signs (pulse rate, bp, respiratory rate, and oral temperature)	X	X			X ⁶						X ⁷									(X)	X	
⁶Vitals assessed at screening (triplicate measurements for pulse and bp) and admission (single measurements). During treatment period vitals assessed predose (triplicate measurements for pulse and bp) and postdose (single measurements) every 15 min for 1 hr, hourly up to 6 hr, and at 12 hr, 24 hr, 36 hr, 48 hr, and 72 hr post-dose
 
⁷Vitals assessed once every 24 hr
 
See Section 8.2.2. in Protocol for further information

Randomization				X																		

Part B – Repeat Dose																													
Procedure	Screening (up to 30 days before Day 1)	Intervention Period [Days] (for each dosing cohort)																	E.D	Follow- up (~14±1 days post last dose)	Notes E.D = early discontinuation/withdrawal								
		-2	-1	1	2	3	4	5-7	8	9-11	12	13-14	15	16	17	18	19	20											
Genetic sample				X																							Any time predose on Day 1 This research may be described in a separate ICF or as part of a combined ICF. A separate signature is required where participant participation is optional		
Study intervention				X			←=====X=====→																						
Telemetry				X																							Telemetry performed starting 30 (±10 min) pre-dose to 12 hr (±20 min) post-dose		
AE review							←=====X=====→																						
SAE review					←=====X=====→																								
Concomitant medication review					←=====X=====→																								

Part B – Repeat Dose																					
Procedure	Screening (up to 30 days before Day 1)	Intervention Period [Days] (for each dosing cohort)																E.D	Follow-up (~14±1 days post last dose)	Notes E.D = early discontinuation/withdrawal	
		-2	-1	1	2	3	4	5-7	8	9-11	12	13-14	15	16	17	18	19				20
Urine sampling PD			X ⁸	X ⁹	X ⁹						X ^{9, 10}									(X)	
⁸combined void for windows of 24-22 hr, 22-20 hr, 20-18 hr, 18-16 hr, 16-12 hr, and 12-0 hr predose.
 
⁹combined void for windows of 0-2 hr, 2-4 hr, 4-6 hr, 6-8 hr, 8-12 hr, and 12-24 hr post-dose
 
¹⁰Day 10 only
 
Aliquots will be removed prior to pooling for urine PK. Total urine volume will be recorded before aliquots for PD are removed.

Part B – Repeat Dose																				
Procedure	Screening (up to 30 days before Day 1)	Intervention Period [Days] (for each dosing cohort)																E.D	Follow-up (~14±1 days post last dose)	Notes E.D = early discontinuation/withdrawal
		-2	-1	1	2	3	4	5-7	8	9-11	12	13-14	15	16	17	18	19			
Blood sampling for PK					X ¹¹			X ¹²		X ¹²				X ¹²			X ¹¹		(X)	¹¹ Day 1 and Day 17: Predose, 5 min, 30 min, 1 hr, 1.5hr, 2 hr, 3 hr, 4 hr, 6 hr, 8 hr, 10 hr, 12 hr, 18 hr, 24 hr, 36 hr, 48 hr, 60 hr, and 72 hr post-dose ¹² pre-dose samples collected on days 6,7, 9-11 and 15-16
Blood sampling for metabolite profiling					X												X			Day 1 and Day 17: Predose, 5 min, 30 min, 1 hr, 1.5 hr, 2 hr, 3 hr, 4 hr, 6 hr, 8 hr, 10 hr, 12 hr, 18 hr, 24 hr, 36 hr, 48 hr, 60 hr, and 72 hr post-dose
Blood sampling for Pharmacodynamics and biomarkers				X ¹³	X ¹³					X ¹⁴							X ¹⁴		(X)	¹³ Predose and 24 hr post-dose on Day 1 ¹⁴ Predose Days 10 and 17

- The timing and number of planned study assessments, including safety, PK, PD/biomarker or other assessments may be altered during the course of the study based on newly available data (e.g., to obtain data closer to the time of peak plasma concentrations) to ensure appropriate monitoring.

Any changes in the timing or addition of time points for any planned study assessments as the result of emerging pharmacokinetic/pharmacodynamic data from this study must be documented and approved by the relevant study team member and then archived in the sponsor and site study files, but will not constitute a protocol amendment. The CA and EC will be informed of any safety issues that constitute a substantial amendment and require alteration of the safety monitoring scheme or amendment of the ICF. The changes will be approved by the CA and the EC before implementation.

Part B .2- 7 Day Repeat Dose																					
Procedure	Screening (up to 30 days before Day 1)	Intervention Period [Days] (for each dosing cohort)															E.D	Follow-up (~14±1 days post last dose)	Notes E.D = early discontinuation/withdrawal		
		-2	-1	1	2	3	4	5	6	7	8	9	10	11	12	13					
Informed consent	X																				
Inclusion and exclusion criteria (including drug screens)	X	X																		Recheck clinical status before randomization and prior to muscle biopsy/or 1st dose of study medication.	
Demography	X																				
Full physical examination including height and weight	F	B																B	(B)	F	F: Full exam; B: Brief exam; height is only taken once at screening
Medical history (includes substance usage and family history of premature CV disease and any changes in health status occurring between screening and admission to the unit)	X	X																			Substances: Drugs, Alcohol, tobacco, and caffeine

Part B .2- 7 Day Repeat Dose																					
Procedure	Screening (up to 30 days before Day 1)			Intervention Period [Days] (for each dosing cohort)													E.D	Follow-up (~14±1 days post last dose)	Notes E.D = early discontinuation/withdrawal		
				-2	-1	1	2	3	4	5	6	7	8	9	10	11				12	13
Past and current medical conditions	X	X																			
HIV, Hepatitis B and C screening	X																		If test otherwise performed within 3 months prior to first dose of study intervention, testing at screening is not required		
Admission to Clinical Unit		X																			
Safety Laboratory assessments (include liver chemistries)	X	X			X							X ¹						X ¹	(X)	X ¹	Pre-randomization assessments for eligibility must be performed PRIOR to predose muscle biopsy Predose, 24 hr, and 48, and 72 hr post-Day 1 dose; additional timepoints may be added based on findings in Part A ¹ Days 7, 10, 13, and follow-up

Part B .2- 7 Day Repeat Dose																				
Procedure	Screening (up to 30 days before Day 1)			Intervention Period [Days] (for each dosing cohort)													E.D	Follow-up (~14±1 days post last dose)	Notes E.D = early discontinuation/withdrawal	
		-2	-1	1	2	3	4	5	6	7	8	9	10	11	12	13				
Routine urinalysis	X	X		X														(X)	X ²	Predose, 24 hr, 48 hr, and 72 hr post-Day 1 dose; additional timepoints may be added based on findings in Part A ² Days 7, 10, 13, and follow-up

Part B .2- 7 Day Repeat Dose																					
Procedure	Screening (up to 30 days before Day 1)			Intervention Period [Days] (for each dosing cohort)														E.D	Follow-up (~14±1 days post last dose)	Notes E.D = early discontinuation/withdrawal	
				-2	-1	1	2	3	4	5	6	7	8	9	10	11	12				13
12-lead ECG	X	X																	(X)	X ⁵	
ECGs assessed at screening (triplicate measure) and admission (single measure). During treatment period ECGs assessed predose (triplicate measure at at least 5 min intervals) and post-dose (single measure) every 30 min for 1 hr, hourly up to 6 hr, at 12 hr post-dose then at 24 hr, 36 hr, 48 hr, and 72 hr post-dose
 
⁵ Days 7,10, 13, and Follow-up Post-dose at Cmax based on observed Cmax in Part A (currently estimated to occur at ~2 hr post dose), except for Day 13 . Day 13 ECG to occur any time before Discharge

Part B .2- 7 Day Repeat Dose																				
Procedure	Screening (up to 30 days before Day 1)			Intervention Period [Days] (for each dosing cohort)														E.D	Follow-up (~14±1 days post last dose)	Notes E.D = early discontinuation/withdrawal
				-2	-1	1	2	3	4	5	6	7	8	9	10	11	12			
Vital signs (pulse rate, bp, respiratory rate, and oral temperature)	X	X			X ⁶								X ⁷				X ⁶	(X)	X	⁶ Vitals assessed at screening (triplicate measurements for pulse and bp) and admission (single measurements). During treatment period vitals assessed predose (triplicate measurements for pulse and bp) and postdose (single measurements) every 15 min for 1 hr, hourly up to 6 hr, and at 12 hr, 24 hr, 36 hr, 48 hr, and 72 hr post-dose ⁷ Vitals assessed once every 24 hr See Section 8.2.2. in Protocol for further information
Randomization				X																

Part B .2- 7 Day Repeat Dose																					
Procedure	Screening (up to 30 days before Day 1)			Intervention Period [Days] (for each dosing cohort)														E.D	Follow-up (~14±1 days post last dose)	Notes E.D = early discontinuation/withdrawal	
		-2	-1	1	2	3	4	5	6	7	8	9	10	11	12	13					
